8.2 Sample Procurement

8.2.1 Pre-SBRT Biopsy Sample

Pre-SBRT biopsy samples will be obtained at time of diagnostic biopsy and will consist of a minimum of two core biopsies.

- **Required collection of archival tumor biopsy tissue (either from initial diagnosis of lung cancer done prior to any study intervention or from any subsequent biopsy), for translational studies.**
A formalin-fixed paraffin-embedded (FFPE) tumor specimen in a paraffin block (preferred) or at least 15 slides containing unstained, freshly cut, serial sections should be submitted along with an associated pathology report prior to study enrollment. If only 10 to 14 slides are available, the specimen may still be used, after Principal Investigator confirmation has been obtained.
- **Required fresh tumor biopsy for translational studies.**
If archival tumor tissue is unavailable or is determined to be unsuitable for required testing, if participant consents, then fresh tumor tissue can be obtained from a biopsy performed after screening.

If participant does not consent, they cannot participate in this study.

Refer to Lab Manual for additional information on tumor specimens collected at screening.

8.2.2 Surgical Sample

Post-assessment by pathologist and verification that adequate tissue has been obtained for clinical use, the remainder of the tumor tissue will be processed for translational studies as defined in study laboratory manual.

9 STUDY PROCEDURES AND SCHEDULE

9.1 Screening/Enrollment/Baseline

SCREENING VISIT

- Informed Consent
- Cancer history
- Demographics - including date of birth, gender, race, and zip code
- Review participant eligibility criteria to ensure participant qualification for study entry
- Physical exam to include vital signs, weight and height at baseline – which helps in the evaluation for surgical candidacy
- Baseline medical history to aid in assessment of possible adverse events
- ECOG Performance Status
- Pulmonary function test
- CBC with differential (± 3 Days)
- CMP (Serum chemistries) (± 3 Days) Serum chemistries to include: albumin, alkaline phosphatase, ALT/SGPT, AST/SGOT, BUN, creatinine, electrolytes (sodium, potassium, calcium, chloride, bicarbonate), glucose, total bilirubin, magnesium, lactate dehydrogenase (LDH), phosphate
- Urinalysis(± 3 Days)

- Urine pregnancy test (women only) (\pm 7 Days)
- Imaging (Chest) – CT preferred.
 - IV and oral contrast will be used for all imaging unless contraindicated. In the event the participant is intolerant to the contrast agent, an alternative imaging modality may be used. If CT contraindicated – MRI will be allowed (IV contrast will be used unless contraindicated). The same type of imaging used at screening must continue to be used throughout the study. Studies will be evaluated using RECIST Version 1.1.²²
- **Required collection of archival tumor biopsy tissue (either from initial diagnosis of lung cancer done prior to any study intervention or from any subsequent biopsy), for translational studies.**

A formalin-fixed paraffin-embedded (FFPE) tumor specimen in a paraffin block (preferred) or at least 15 slides containing unstained, freshly cut, serial sections should be submitted along with an associated pathology report prior to study enrollment. If only 10 to 14 slides are available, the specimen may still be used, after Principal Investigator confirmation has been obtained.
- **Required fresh tumor biopsy for translational studies.**

If archival tumor tissue is unavailable or is determined to be unsuitable for required testing, if participant consents, then fresh tumor tissue can be obtained from a biopsy performed after screening.

If participant does not consent, they cannot participate in this study.

Refer to Lab Manual for additional information on tumor specimens collected at screening.

At any time after enrollment and before surgery

Pre-operative anesthesia clinic clearance for surgery is required and *may* include

- EKG
- Stress Test
- Cardiac Clearance

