4 STUDY DESIGN

4.1 Overall Design

This is a single arm pilot study. Participants with medically operable NSCLC will receive SBRT 800 cGy X 3 fractions delivered 5-7 days prior to planned surgery.

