5.1 Inclusion Criteria

PARTICIPANT MRN		PARTICIPANT INITIALS
Verified	Criteria	
	5.1.1	Ability of participant OR Legally Authorized Representative (LAR) to understand this study, and participant or LAR willingness to sign a written informed consent
	5.1.2	Males and females age ≥ 18 years
	5.1.3	ECOG Performance Status 0 - 1 (Appendix A.)
	5.1.4	Women of childbearing potential must have a negative serum pregnancy test 48 hours prior to initiating study intervention.
	5.1.5	Histological confirmation of Stage I or II NSCLC
	5.1.6	Candidate for oncologic surgery (lobectomy or sub lobar resection)

PARTICIPANT MRN		PARTICIPANT INITIALS		
Verified	Criteria			
	5.1.7	Adequate diagnostic biopsy tissue to allow for pre-SBRT tumor analysis		
	5.1.7	Lesion must be located peripherally, ≥ 2 cm from bronchial margin and 1 cm from visceral pleura with location deemed acceptable by cardiothoracic surgeon for resection.		
	5.1.8	Pulmonary function: Baseline PFTs including adequate FEV1 deemed by cardiothoracic surgeon to be acceptable for oncologic surgery, with a predicted post-operative FEV1 of 40% or greater and DLCO of 40% or greater.		
Adequate organ function, defined as follows:		Result	Date	
		White blood cell (WBC) count $\geq 3.0 \times 10^3$ cells/mm ³		
		Hemoglobin ≥ 10 g/dL		
		Absolute Neutrophil Count ≥ 1.5 K/UL		
		Platelets ≥ 150 K/UL		
		Serum creatinine clearance > 50 mL/min		
		Total bilirubin $\leq 2.0 \times$ ULN		
		Aspartate aminotransferase and alanine aminotransferase $\leq 2.5 \times$ ULN		
		Women of child-bearing potential and men with partners of child-bearing potential must agree to practice sexual abstinence or to use the forms of contraception listed in Child-Bearing Potential/Pregnancy section for the duration of study participation and for 6 months following completion of therapy.		

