5.2 Exclusion Criteria

Participants meeting any of the exclusion criteria listed below at screening will be excluded from study participation.

PARTICIPANT MRN		PARTICIPANT INITIALS
No	Criteria	
	5.2.1	Simultaneously enrolled in any therapeutic clinical trial
	5.2.2	Diagnosed with a psychiatric illness or is in a social situation that would limit compliance with study requirements
	5.2.3	Is pregnant or breastfeeding
	5.2.4	Prior history of lung/chest wall surgery
	5.2.5	Prior history of radiation treatment to the chest
	5.2.6	History of autoimmune disease
	5.2.7	Current use of immunosuppressive drugs
	5.2.8	Prior history of immunotherapy
	5.2.9	Prior history of metastatic cancer or concurrent active secondary malignancy

Eligibility Confirmed	Print Name	Signature	Date
Clinical Research Coordinator			
Double Check			
Treating Physician			

Once eligibility has been confirmed, use the link below to register your participant.
 Please allow up to 24 business hours for the registration process.

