9.1.1 Procedures During Study Intervention

Day 0 - Simulation

- Radiation Simulation
- Adverse event assessment

Day 1 – Prior to 1st fraction

- Blood collection for translational studies

Day 1 – 1st Fraction

- Radiation – Fraction 1
- Adverse event assessment

Day 2 – 2nd Fraction

- Radiation – Fraction 2
- Adverse event assessment

Day 3 – 3rd Fraction

- Radiation – Fraction 3
- Adverse event assessment

NOTE: There is a 5-7 day rest period after radiation and before surgery.

Day of Surgery (Occurs during days 8-10)

- ECOG
- CBC with Differential (± 3 Days)
- CMP (Serum Chemistries) (± 3 Days)
- Physical exam
- Adverse event assessment
- Peri-operative surgical complication assessment
- Blood collection for translational studies BEFORE surgery
- Surgical specimen collection

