9.3 SCHEDULE OF EVENTS TABLE

Screening Period	Screening & Baseline	Day 0	Day 1	Day 2	Day 3	Days 8 – 10	Post-Operative Follow Up				
		Simulation	1 st Fraction	2 nd Fraction	3 rd Fraction	Surgery	24 Hours	Day of Discharge	1-3weeks	6 months	Every 6 months after surgery (Last follow up at 36 months)
Simulation		X									
SBRT			X	X	X						
Informed Consent	X										
Cancer History	X										
Demographics	X										
Inclusion/Exclusion	X										
Physical Exam	X					X	X	X	X	X	X
ECOG Performance Status (PS)	X					X					
Pre-Op Anesthesia Clearance	To be completed before surgery										
PFT	X										
Adverse Event Assessment	X (Med Hx Review)	X	X	X	X	X	X	X	X	X	X
Peri- / Post-Operative Surgical Complication Assessment						X	X	X	X	X	
Wound Healing Assessment								X	X	X	
CBC with Diff	X					X Before Surgery	X				
CMP (Serum Chemistries)	X					X Before Surgery					
BMP							X				
Urinalysis	X										
Pregnancy (URINE) Test	X										

Screening Period	Screening & Baseline	Day 0	Day 1	Day 2	Day 3	Days 8 – 10	Post-Operative Follow Up				
		Simulation	1 st Fraction	2 nd Fraction	3 rd Fraction	Surgery	24 Hours	Day of Discharge	1-3weeks	6 months	Every 6 months after surgery (Last follow up at 36 months)
Pregnancy Status Check										X	
CT Imaging of chest	X									X	X
Chest X-Ray							X		X		
Blood Collection for Translational Studies	X		X Before SBRT			X Before Surgery		X			
Tumor Tissue Collection	X (Archival)					X (Surgical Specimen)					

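### The required anesthesia clearance may be completed after all three SBRT fractions; it should be a condition of fraction 1

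*Protocol*

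**What the plan says.** Protocol section 9.1 states that "Pre-operative anesthesia clinic clearance for surgery is required" and lists an EKG, a stress test and cardiac clearance as things it may include. The heading over that item sets the window: "At any time after enrollment and before surgery". The schedule of events in section 9.3 agrees. It gives the clearance no visit column and says only "To be completed before surgery".

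On the timeline, section 9.1.1 puts the fractions on Days 1, 2 and 3 and notes that "There is a 5-7 day rest period after radiation and before surgery", with surgery on Days 8-10. Section 4.1 describes the sequence as follows: "Participants with medically operable NSCLC will receive SBRT 800 cGy X 3 fractions delivered 5-7 days prior to planned surgery".

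On fitness at entry, section 5.1 requires a candidate for lobectomy or sublobar resection, a lesion location acceptable to the cardiothoracic surgeon, and pulmonary function "deemed by cardiothoracic surgeon to be acceptable for oncologic surgery" with predicted post-operative FEV1 and DLCO of at least 40%. It also requires ECOG 0-1 and organ-function limits. Section 7 requires all criteria to be met for registration, and registration before therapy.

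**The concern.** The radiation in this trial is justified as a step before an operation. The dose is deliberately non-ablative: section 1.3.3 contrasts 800 cGy x 3 with the 1800-2000 cGy x 3 that it calls the most common SBRT regimen for NSCLC. A participant who is irradiated and then not resected has had study radiation to the chest without the planned resection and still needs definitive care.

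The sections quoted above allow a required surgical check to be completed after that radiation has been given. If the check then fails or calls for more work-up, one of two things follows.

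- **Surgery is cancelled.** The participant has been irradiated without the planned resection and provides no surgical specimen for the paired primary endpoint (section 3.3).
- **Surgery is delayed.** Resection still happens but may fall outside the 5-7 days stated in sections 2, 4.1 and 8.1, so the post-SBRT tissue is taken at the wrong time.

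The first bears on participant protection. The second concerns tissue timing only.

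**Working it through.** The Protocol states no figure on this point to reproduce. The check sets the sections side by side and then does some calendar arithmetic.

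**1. Is a late clearance compliant?** Fraction 3 is on Day 3 and the rest period is 5-7 days. Day 3 + 5 = Day 8 and Day 3 + 7 = Day 10, which matches the surgery days in sections 9.1.1 and 9.3. The clearance window runs from enrollment to surgery, so it includes Days 1-3 and the whole rest period. A clearance in the rest period is compliant, after 3 x 8 Gy = 24 Gy.

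**2. Does another rule close the gap?**

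| Place in the Protocol | What it requires before fraction 1 | Anesthesia clearance named? |
|---|---|---|
| 5.1 Inclusion | Surgical candidacy, location, pulmonary function, ECOG 0-1, organ function | No |
| 5.2 Exclusion | Screening exclusions; no cardiac exclusion is listed | No |
| 7.1-7.2 Registration | All criteria met; registration before therapy | No |
| 8.1 Quality assurance | Team discussion, dose homogeneity, organ-at-risk dose limits | No |
| 9.1.1 Day 0 | Simulation, adverse event assessment | No |
| 9.1.1 Day 1, before the 1st fraction | Research blood collection | No |

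None does. Because the window opens only after enrollment, the clearance as written lies outside the eligibility decision.

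**3. How much room does a late clearance leave?** Assumption: fractions, clinic and surgery all fall Monday to Friday, with no holidays. Counted are the working days strictly between fraction 3 and surgery.

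| Fraction days | Weekday surgery options after fraction 3 | Working days between |
|---|---|---|
| Mon-Wed, Tue-Thu or Wed-Fri | +5, +6, +7 days | 2, 3, 4 |
| Mon/Wed/Fri | +5, +6, +7 days | 2, 3, 4 |
| Thu/Fri/Mon | +7 days only | 4 |
| Fri/Mon/Tue | +6, +7 days | 3, 4 |

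So 2-4 working days remain for the clinic visit and any cardiac work-up. The Protocol does not say how long these take, so the count describes the room and does not show that it is too short.

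**4. What does one cancelled operation cost?** With 10 planned participants, the result is either 10 - 1 = 9 tissue pairs without replacement, or 10 + 1 = 11 people irradiated for 10 resections with replacement. These are alternatives. Section 6.2 rules out replacement only after completed surgery, which implies that it is possible before then.

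**5. How old is an early clearance at surgery?** For a clearance obtained on Day 1, age = (days from fraction 1 to fraction 3) + (days from fraction 3 to surgery).

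- Consecutive fractions: 2 + (5 to 7) = 7-9 days.
- Alternate-day (Mon/Wed/Fri): 4 + (5 to 7) = 9-11 days.
- Weekend-split: Thu/Fri/Mon gives 4 + 7 = 11 days; Fri/Mon/Tue gives 4 + (6 to 7) = 10-11 days. Together, 10-11 days.

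Section 8.1 sets a minimum of 18 hours between fractions but no maximum, so a more stretched schedule would make the clearance older.

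**The case against.** The strongest case on the other side has four parts.

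**Operability is already checked before SBRT.** This largely stands. Section 5.1 requires surgical candidacy and the surgeon's acceptance of location and lung function, and section 9.1 adds a physical examination that helps assess surgical candidacy. A reader might infer that the Protocol irradiates people whose operability is unknown, or that section 4.1 is contradicted. The text does not support either: participants who meet section 5.1 can fairly be called medically operable. What remains is that the clearance is a separate required step, which may bring in cardiac testing that section 5.1 does not name.

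**The wording is permissive and consistent.** This stands. Sections 9.1 and 9.3 agree, early clearance is allowed, and late clearance is not directed. Sites may already obtain it early. The point is only that the late slot is permitted.

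**The harm needs a chain of events and is partly handled.** This stands as to likelihood. The site must use the late slot, an accepted surgical candidate must then fail or stall, and surgery must be cancelled or moved out of its interval. Replacement appears possible, section 9.5 provides for alternative care and continued safety follow-up, and section 8.1 anticipates organ toxicity below 1%. None of this reverses radiation already given.

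**An earlier clearance is a trade-off.** This also stands. A clearance closer to surgery reflects fitness after SBRT; one before fraction 1 does not. The day-of-surgery assessment offsets this only in part, because it is not a second anesthesia clearance.

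**Conclusion.** The point holds as a minor one. The Protocol permits a required pre-surgical clearance to be completed after 24 Gy has been delivered, and nothing else in it makes the clearance a condition of fraction 1. The consequence for a participant who then fails clearance cannot be undone, while the rule that would prevent it adds no procedure.

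The likelihood is unknown and probably low after the section 5.1 screening. Any probability of at least one such case among 10 participants would rest on an assumed failure rate and on every failure occurring after SBRT; the Protocol supports neither. A reader might also infer a loss of power. That does not follow, because section 2 says the analysis is descriptive with no formal hypothesis testing. The countable effect is one tissue pair, or one additional irradiated participant, per cancelled operation. The calendar figures assume weekday scheduling without holidays.

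**What to change.** Four edits to the Protocol:

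- Section 9.1: change the heading over the clearance item to *After enrollment and before the first SBRT fraction*. The starting point stays at enrollment, so no anesthesia visit is needed before eligibility is confirmed.
- Section 9.3: replace the entry in the clearance row with *To be completed before fraction 1*.
- Section 9.1.1: under Day 1, before the 1st fraction, add *anesthesia clearance documented*.
- Section 9.1.1, day of surgery: keep the existing physical examination, ECOG, CBC and CMP, and state that they are also used to look for change since the clearance.

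The content of the clearance stays as it is. The cost is wording, earlier clinic booking, possibly a short delay to SBRT, and an older clearance that reflects fitness before radiation. A change in condition after SBRT could still cancel or delay surgery, and the edits do not remove that risk.

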9.1.1 Procedures During Study Intervention

Day 0 - Simulation

- Radiation Simulation
- Adverse event assessment

Day 1 – Prior to 1st fraction

- Blood collection for translational studies

Day 1 – 1st Fraction

- Radiation – Fraction 1
- Adverse event assessment

Day 2 – 2nd Fraction

- Radiation – Fraction 2
- Adverse event assessment

Day 3 – 3rd Fraction

- Radiation – Fraction 3
- Adverse event assessment

NOTE: There is a 5-7 day rest period after radiation and before surgery.

Day of Surgery (Occurs during days 8-10)

- ECOG
- CBC with Differential (± 3 Days)
- CMP (Serum Chemistries) (± 3 Days)
- Physical exam
- Adverse event assessment
- Peri-operative surgical complication assessment
- Blood collection for translational studies BEFORE surgery
- Surgical specimen collection

9.1.2 Follow-Up Visits

POST OPERATIVE FOLLOW UP

24 Hours post-op

- Physical exam
- Adverse event assessment
- Post-operative surgical complication assessment
- CBC with Differential (± 3 Days)
- Basic Metabolic Panel (BMP) (± 3 Days)
- Post-operative chest x-ray (within 24 hours of surgery)

Day of Discharge (post-op)

- Physical exam
- Adverse event assessment
- Post-operative surgical complication assessment
- Wound healing assessment
- Blood collection for translational studies

- **1-3 weeks post-op** Physical exam
- Adverse event assessment
- Post-operative surgical complication assessment
- Wound healing assessment
- Chest X-Ray (CXR)

6 Months (post-op) (\pm 2 months)

- Imaging (Chest) – CT preferred.
 - IV and oral contrast will be used for all imaging unless contraindicated. In the event the participant is intolerant to the contrast agent, an alternative imaging modality may be used. If CT contraindicated – MRI will be allowed (IV contrast will be used unless contraindicated). The same type of imaging used at screening must continue to be used throughout the study. Studies will be evaluated using RECIST Version 1.1.
- Physical exam
- Adverse event assessment
- Post-operative surgical complication assessment
- Wound healing assessment
- Check pregnancy status

Every 6 months (\pm 2 months) after initial 6-month follow up**Last study follow up at month 36 after enrollment**

- Imaging (Chest) – CT preferred.
 - IV AND oral contrast will be used for all imaging unless contraindicated. In the event the participant is intolerant to the contrast agent, an alternative imaging modality may be used. If CT contraindicated. The same type of imaging used at screening must continue to be used throughout the study. Studies will be evaluated using RECIST Version 1.1
- Physical exam
- Adverse event assessment

9.2 Lost to Follow Up

Institution policy will be followed for participants considered lost to follow up.

9.3 SCHEDULE OF EVENTS TABLE

Screening Period	Screening & Baseline	Day 0	Day 1	Day 2	Day 3	Days 8 – 10	Post-Operative Follow Up				
		Simulation	1 st Fraction	2 nd Fraction	3 rd Fraction	Surgery	24 Hours	Day of Discharge	1-3weeks	6 months	Every 6 months after surgery (Last follow up at 36 months)
Simulation		X									
SBRT			X	X	X						
Informed Consent	X										
Cancer History	X										
Demographics	X										
Inclusion/Exclusion	X										
Physical Exam	X					X	X	X	X	X	X
ECOG Performance Status (PS)	X					X					
Pre-Op Anesthesia Clearance	To be completed before surgery										
PFT	X										
Adverse Event Assessment	X (Med Hx Review)	X	X	X	X	X	X	X	X	X	X
Peri- / Post-Operative Surgical Complication Assessment						X	X	X	X	X	
Wound Healing Assessment								X	X	X	
CBC with Diff	X					X Before Surgery	X				
CMP (Serum Chemistries)	X					X Before Surgery					
BMP							X				
Urinalysis	X										
Pregnancy (URINE) Test	X										

Screening Period	Screening & Baseline	Day 0	Day 1	Day 2	Day 3	Days 8 – 10	Post-Operative Follow Up				
		Simulation	1 st Fraction	2 nd Fraction	3 rd Fraction	Surgery	24 Hours	Day of Discharge	1-3weeks	6 months	Every 6 months after surgery (Last follow up at 36 months)
Pregnancy Status Check										X	
CT Imaging of chest	X									X	X
Chest X-Ray							X		X		
Blood Collection for Translational Studies	X		X Before SBRT			X Before Surgery		X			
Tumor Tissue Collection	X (Archival)					X (Surgical Specimen)					

9.4 Supportive Care Guidelines

Therapies required for standard supporting care following surgery is acceptable.

9.4.1 Prohibited or Restricted Concomitant Medications

We strongly encourage physicians to avoid use of immunosuppressive medications up to 1 month following surgery as this can affect surgical wound healing and may alter the immune microenvironment.

9.4.2 Diet

No dietary modifications required in this study.

9.5 Participant Discontinuation/Withdrawal from the Study

Duration of therapy will depend on individual response, evidence of disease progression and tolerance. Participants may be withdrawn from the study intervention if any of the following occur:

- Intercurrent illness that prevents further administration of study intervention.
- Unacceptable adverse event(s).
- Participant decides to withdraw from the protocol therapy.
- General or specific changes in the participant's condition render the participant unacceptable for further study intervention in the judgment of the treating investigator.
- Major violation of the study protocol (i.e., unable to adhere to study schedule) that in the opinion of the treating investigator, puts the participant at undue risk.
- Discontinuation of the study by The University of Kansas Cancer Center.
- Confirmed pregnancy.
- Completed follow up as per protocol
- Lost to follow-up.
- Death

Participants will be removed from the protocol therapy when any of these criteria apply. The reason for removal from protocol therapy, and the date the participant was removed, must be documented in the electronic case report form (eCRF). Alternative care options will be discussed with the participant. Safety monitoring and follow-up assessments should continue as appropriate according to the study schedule, unless the participant has withdrawn consent for study participation. Participants removed from protocol therapy for unacceptable adverse event(s) will be followed until resolution or stabilization of the adverse event.

When a participant is removed from protocol therapy and/or is off of the study, the relevant Off-Treatment/Off-Study information will be updated in CRIS.

In the event of unusual or life-threatening complications, treating investigators must immediately notify the Sponsor/Investigator.

